9.1.2 CONFIDENTIALITY AND PRIVACY

Information will be treated in strict confidentiality to protect the privacy of patients. The investigators will have no access to the data of the patient, except the one provided by the GP meaning that the only person to know who is being studied is the GP.

Data will be electronically stored in a database specifically designed for this study using MS Access 2010. Data will be encrypted and password protected.

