1 PROTOCOL SUMMARY

1.1 SYNOPSIS

Title:	Deprescribing: a portrait and out-comes of the reduction of Polypharmacy in Portugal (DePil17-20)
Study Description:	This study protocol comprises three phases. The first two phases will be nationwide and aim to evaluate the prevalence and patterns of polypharmacy and assess the barriers and facilitators of deprescribing perceived by older adults, as well as their willingness to be deprescribed and to self-medicate. The third and last phase will be a non-pharmacological randomised clinical study to measure the impact of enablement of older adults in their willingness to be deprescribed and related quality of life.
Objectives:	Primary Objective: Willingness to be deprescribed after the intervention Secondary Objectives: Quality of life after the intervention
Study Population:	Older adults (≥ 65 years) in Portugal
Description of Study	In the intervention group the investigators will give enablement tools and talks with their General Practitioners about how to issue the problem of polypharmacy.
Intervention:	
Study Duration:	36 months.
Participant Duration:	6 month.

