Perception of medication will be evaluated using Portuguese general BMQ, the willingness to be deprescribed will be assessed with two open-questions (one to assess the facilitators and the other to assess the barriers), and the actual self-medication will be evaluated with an analogic visual scale (0 to 10) about the need to self-medicate and its justification.

For those not knowing how to write or read, someone of their knowledge, will fill in the open questions, with their answers.

In case of less than 5% of answers of the open questions, two patient groups will be invited to make a focus group asserting reasons for accepting deprescribing.

Phase III: impact of enablement of older adults in their willingness to deprescribe and quality of life

Design

Non-pharmacological randomised clinical study, intended to last for six months.

Setting

Primary Care Centres in Portugal will be randomly selected from six Health Centres of Centre of Portugal (Aveiro, Castelo Branco, Coimbra, Guarda, Leiria and Viseu)

Sample size

Will be created two groups with a minimum of 190 patients each (one will be the intervention group and the other the control).

Study procedures

This phase of the study is expected to start in September 2019 and will last for 6 months.

Again, GPs sampling will be made according to existing files and those who accept to participate will recruit their own patients. Patients from previous phases can be enrolled in phase III. Assuming that a GP will be able to include at least 6 patients, a total of 64 GPs has to be enrolled in the study. Enrolled GPs will be instructed to invite all older adult (≥ 65 years) patients attending to the primary care consultation to participate in the study during until obtaining the sample size and being randomized according to the table for study entry. The geographical areas of work, the Districts, will be randomized for entry into exposed and unexposed groups. Those patients willing to participate in the study must give written informed consent and present willingness and ability to comply with the study requirements.

Exclusion criteria: Being acutely unwell in the last three weeks, and refuse to participate.

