Two groups will be created with a minimum of 190 patients each, one of which will be composed from patients from the region of Aveiro, Coimbra and Guarda and the other from patients from the region of Castelo Branco, Leiria and Viseu. In the intervention group we will give enablement tools and talks with their GPs about how to issue the problem of polypharmacy. The information given in this group will result from the knowledge obtained in phase II in the shape of small leaflets and other information materials to be made according to the best practice, to be given and remembered at scheduled times to the intervention group.

Data collection

The collection of the data will occur in the beginning and end of phase II.

Patient's socio-demographic and clinical characteristics and medication will be registered using the same methodology as described in phase I.

Perception of medication will be evaluated using Portuguese general BMQ, the willingness to be deprescribed will be assessed with two open-questions (the same as phase II), and the quality of life we will assessed with EQ-5D.

For those not knowing how to write, someone of their knowledge, will fill in the open questions.

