7 STUDY ASSESSMENTS AND PROCEDURES

7.1 EFFICACY ASSESSMENTS

List and description of the procedures/evaluations to be used:

- Portuguese Beliefs about Medicines Questionnaire
 - For evaluation of the perception of medication
- EuroQol Five Dimensions Questionnaire
 - For assessment of the quality of life
- Two open-questions (one to assess the facilitators and the other to assess the barriers)
 - For assessment of the willingness to be deprescribed

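### In Phase III the patient's own GP is the only route for the data and, in the intervention arm only, is involved in the intervention, so stated willingness can be biased differently by arm

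*Protocol*

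**What the plan says.** The synopsis gives the primary aim as "Primary Objective: Willingness to be deprescribed after the intervention". For Phase III, section 4 states that "the willingness to be deprescribed will be assessed with two open-questions (the same as phase II", and section 7.1 lists the same two questions, one on facilitators and one on barriers, as the only instrument for willingness. Quality of life, the secondary aim, is measured with the EQ-5D, also by self-report. Medication is recorded too, but drugs actually stopped are not a primary or secondary objective.

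Three provisions place the patient's own GP around this outcome:

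- **Recruitment.** Under Phase III study procedures, participating GPs recruit their own patients.
- **Intervention.** Sections 4 and 6 say "In the intervention group we will give enablement tools and talks with their GPs about how to issue the problem of polypharmacy". No such provision is made for the control group.
- **Data route.** Section 9.1.2, repeating a sentence from Phase I data collection in section 4, says "The investigators will have no access to the data of the patient, except the one provided by the GP" and adds that "the only person to know who is being studied is the GP".

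On completion of the forms, the Phase III text says only this: "For those not knowing how to write, someone of their knowledge, will fill in the open questions". It does not say who hands out, collects or reads the answers.

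**The concern.** Willingness is an attitude that the patient states. A patient who knows, or supposes, that the GP will see the answer may shade it towards what the GP seems to want. In the intervention arm there is a clear expected answer, because the patient has received material on reducing medicines and the GP is involved in that effort. In the control arm the GP also passes on the answers, but no message of this kind has come with the GP's involvement. The wish to please can therefore be stronger in one arm, and it points the same way as the hypothesis in section 8.1.

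The baseline measurement does not cancel this, because the message arrives after baseline. No objective endpoint is set to check the stated attitude. A favourable difference in willingness could then be hard to tell apart from courtesy towards the GP.

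**Working it through.** **1. Does the GP-only route apply to Phase III?** Section 9.1.2 is a study-wide provision with no phase named, so it does. The sentence in Phase I data collection has the same wording.

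**2. Is the GP involved in the intervention?** The phrase about talks can mean talks between patient and GP, or talks by the investigators with the GPs. The patient's own GP is involved under either reading, and only in the intervention arm. The scheduled reminders are described without saying who gives them, so they are not counted here.

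**3. Are the answers kept from the GP?** The provision for people who cannot write implies that the others write their own answers. No sealed return, independent collector or restriction on who may help is described. The helper is someone the patient knows, which does not exclude practice staff.

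**4. When is it measured?** The Phase III section places data collection at the beginning and end of phase II. I read this as Phase III, since the passage describes the Phase III measures.

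**5. The plan's own figure.** Section 8.2 gives 380 patients for a 95% interval and a 5% margin. With p = 0.5:

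n = 1.96² × 0.5 × 0.5 / 0.05² = 384.1, rounded up to 385.

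The stated 380 is within about 1.3% of this (5/385) and equals 2 × 190. It is not in dispute here.

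**6. Illustration of size.** The protocol gives no control rate, no scoring of the free text and no rate of courtesy answers. Assume a binary outcome (willing or not) and no true effect. Let f be the share of all intervention patients coded willing only because of the GP, over and above any such share among controls. The expected contrast is then f itself:

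- f = 0.05: 0.05 × 190 = 9.5 patients, 5 points.
- f = 0.10: 0.10 × 190 = 19 patients, 10 points.

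This restates the assumption and is not an estimate.

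**7. What such a shift would do to the test.** Take a two-sided pooled two-proportion test at 0.05 with 190 per arm, control rate p and intervention rate p + f. The chance of a significant result favouring the intervention is 1 − Φ[(1.96 × se₀ − f)/se₁], where

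- se₀ = √(2 × p̄(1 − p̄)/190), with p̄ = p + f/2;
- se₁ = √{[p(1 − p) + (p + f)(1 − p − f)]/190}.

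For p = 0.5 and f = 0.05: se₀ = 0.0512, se₁ = 0.0512, the bracket is 0.985 and the probability is 0.162.

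Over assumed control rates of 30%, 50% and 70%:

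| Assumed shift | Chance of a false result for the intervention |
|---|---|
| 0 points | 2.5% |
| 3 points | 8.4% to 9.5% |
| 5 points | 16% to 19% |
| 10 points | 50% to 62% |
| 15 points | 84% to 94% |

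These figures treat patients as independent and ignore the allocation by district. They show how sensitive the test is to a shift, not how large the shift would be.

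**The case against.** The best reply is that section 9.1.2 is a confidentiality rule. It concerns who knows the patients' identities, not how questionnaires are administered. In Phase III, only the socio-demographic, clinical and medication data are tied to the Phase I method, in which the GP collects. The BMQ, open questions and EQ-5D stand in a separate sentence with no collector named. A coded form that the GP merely passes on would satisfy the rule.

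This stands as a limit on the point. A reader might infer that the GP interviews the patient, or that patients tell their answer to the doctor who raised deprescribing with them. The protocol does not say so, and its wording suggests self-completion. A reader might also infer that control patients face no pressure at all. That is too absolute: they too are recruited by their GP and answer through the GP, and section 9.1.1.1 has consent forms describe the intervention in detail. Only a differential part can bias the contrast.

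Two further replies have force. Any figure for the bias is an assumption, and it needs a willing/unwilling scoring that the protocol does not define. Masked coding of free text may also be set out in a statistical analysis plan that is not shown, so its absence from the protocol is not counted as a fault.

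What the reply does not remove is the stated route. Under the protocol's own rule the answers pass through the GP, and nothing keeps them closed. This is a feature of data collection and cannot be repaired at the analysis.

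**Conclusion.** The point holds in a limited form. The protocol routes all Phase III data through the patient's own GP, involves that GP in the intervention in one arm only, and rests its primary outcome on stated willingness with nothing to keep the answers from the GP. This allows a reporting bias that differs by arm and favours the hypothesis.

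The protocol does not show that the bias will occur, and its size cannot be derived from the document. The 5 points per 5% of patients, and the false-positive rates above, depend on an assumed binary outcome, assumed control rates, an assumed differential shift and independent patients. The trial can still be run, but the collection route should be changed because the change is cheap and a positive primary result would otherwise be open to this explanation.

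**What to change.** Amend the Phase III data collection text in section 4, and section 9.1.2, as follows, for both arms and both time points:

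- The patient completes the open questions, BMQ and EQ-5D away from the GP. Where a helper is needed, the helper is neither the GP nor practice staff.
- The forms go into a sealed envelope bearing only the study code. The GP tells the patient that the practice will not read them, and forwards the envelope unopened.
- The free text is coded from a file stripped of district, GP and time point. District matters because each group is made up of three named districts, so the district label reveals the arm. This step may sit in the analysis plan if one exists.

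The confidentiality rule is kept, since only the code leaves the practice and the GP remains the only person who knows the patient's identity. The cost is envelopes, a short amendment and entry of the forms by the study team. The GP can no longer check forms for missing items. Some wish to please the study itself will remain, because patients know that they received the materials.

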9.1.4 PUBLICATION AND DATA SHARING POLICY

The investigators will publish the results in peer-reviewed journal. There is no provision for data sharing.

9.1.5 CONFLICT OF INTEREST POLICY

The investigators don't have any conflict of interest.

9.2 ABBREVIATIONS

ANCOVA	Analysis of Covariance
ANOVA	Analysis of Variance
BMQ	Beliefs about Medicines Questionnaire
CI	Confidence Interval
EQ-5D	EuroQol Five Dimensions Questionnaire
GCP	Good Clinical Practice
GP	General Practitioner
ICH	International Conference on Harmonisation
IRB	Institutional Review Board
PIM	Potentially Inappropriate Medication
START	Screening Tool to Alert Doctors to Right Treatment
STOPP	Screening Tool of Older Person's Prescriptions

